1.1 Synopsis

Protocol Title: A Multicenter, Randomized, Double-blind Study Evaluating the Pharmacokinetics, Efficacy, Safety, and Immunogenicity of Multiple Switches Between Humira® (Adalimumab [US]) and ABP 501 Compared With Continued Use of Adalimumab in Subjects With Moderate to Severe Plaque Psoriasis

Sponsor Protocol No.: 20200497

Study Phase: Phase 3

Sponsor: Amgen Inc.

Rationale

The current study is designed to investigate the pharmacokinetics (PK), efficacy, safety, and immunogenicity of multiple switches between adalimumab (Humira®) and ABP 501 compared with continued use of adalimumab in subjects with moderate to severe plaque psoriasis (Ps).

Objectives and Endpoints:

Objectives	Endpoints
Primary Objective:	Primary Endpoints:
To demonstrate similarity of PK in subjects after multiple switches between adalimumab and ABP 501, compared to subjects receiving continued use of adalimumab.	Pharmacokinetic parameters: AUC _{tau} between week 28 and week 30. C _{max} between week 28 and week 30.
Secondary Objective:	Secondary Endpoints:
To assess the efficacy, safety, and immunogenicity in subjects after multiple switches between ABP 501 and adalimumab compared with subjects receiving continued use of adalimumab.	 Pharmacokinetic related Endpoints: t_{max} between week 28 and week 30. C_{trough} between week 14 and week 28. Efficacy related Endpoints: PASI percent improvement from baseline (day 1) to week 30. PASI 75 response at week 30. PASI 90 response at week 30. PASI 100 response at week 30.
	Safety related Endpoints: Treatment-emergent adverse events and serious adverse events, post randomization. Events of interest, post randomization.

Clinical Study Protocol: 20200497

Final 1.0 Date: 03 Jun 2021 Page **11** of **87**

Objectives	Endpoints						
	Immunogenicity-related Endpoints:						
	Incidence of ADAs, post randomization						

ADAs = antidrug antibodies; AUC $_{tau}$ = area under the curve from time 0 over the dosing interval; C_{max} = maximum concentration; C_{trough} = trough concentration; PASI = Psoriasis Area and Severity Index; t_{max} = time of maximum concentration

Overall Design:

This is a randomized, double-blind, phase 3 study in adult subjects with moderate to severe Ps.

The total duration of study participation for each subject will be about 36 weeks, with up to 4 weeks for screening and approximately 32 weeks after the first investigational product administration.

All enrolled subjects not randomized at week 12 will be considered lead-in failures and the lead-in failure reason will be documented.

An EOS Visit will be conducted at week 32.

Disclosure Statement: This is a parallel group, treatment study with 2 arms that are both subject and investigator blinded.

Clinical Study Protocol: 20200497 Final 1.0 Date: 03 Jun 2021

Final 1.0 Date: 03 Jun 2021 Page **12** of **87**

Number of Arms: Continued-use group

Switching group

Number of Subjects and Statistical Considerations:

Approximately 414 subjects will be enrolled to receive adalimumab during the lead-in period. Subjects with prior biologic use for psoriasis will be capped at 50% of the total enrolled subjects. This sample size will ensure approximately 342 subjects will be randomized at week 12 after the lead-in period, considering 17% lead-in failures, in a 1:1 ratio to the continued-use group or the switching group. The randomization will be stratified by prior biologic use for psoriasis at baseline (week 1/day 1, yes vs. no) and geographic region. The number of subjects enrolled may be adjusted during the study with the actual lead-in failure rate seen to ensure approximately 342 subjects will be randomized at week 12. Subjects already enrolled will be allowed to be randomized at week 12. The sample size of 342 randomized subjects will provide at least 90% power to demonstrate similarity of the primary PK endpoints based on the Two One-Sided Tests at a 0.05 significance level, assuming a between-subject variability (as measured by coefficient of variation) of 53% for ABP 501 and adalimumab, a true geometric mean ratio (GMR) of 1 between ABP 501 and adalimumab, a similarity margin of 0.8, 1.25, and 15% drop-outs after randomization through week 30 (including subjects who discontinue the study prior to week 28 and those reaching week 28 but do not have evaluable primary PK endpoints between weeks 28 and 30).

Intervention Groups and Duration:

The total duration of study participation for each subject will be about 36 weeks, with up to 4 weeks for screening and approximately 32 weeks after the first investigational product administration.

Dose regimens: Continued-use of adalimumab (adalimumab mg or mg, SC injection) and switching group (adalimumab mg or mg, ABP 501 mg, SC injection).

Reference Group: Adalimumab Continued-use Group	Continued-use of adalimumab administered by SC injection using prefilled syringes at a dose of mg (2 x mg loading dose) on week 1/day 1 and mg administered 1 week later at week 2/day 8, then at 2 weeks interval at week 4, week 6, week 8, and week 10. Subsequent dosing will be at mg every 2 weeks thereafter up to and including week 28.						
Test Group: Switching Group	Switching group with adalimumab administered by SC injection using prefilled syringes at a dose of mg (2 x mg loading dose) on week 1/day 1 and mg administered 1 week later at week 2/day 8, then at 2 weeks interval at week 4, week 6, week 8, and week 10. • At week 12, subjects will be switched to ABP 501 and administered ABP 501 mg SC on weeks 12 and 14. • At week 16, subjects will be switched back to adalimumab and administered adalimumab mg SC on weeks 16 and 18. • At week 20, subjects will then be switched to ABP 501 and administered ABP 501 mg SC on weeks 20, 22, 24, 26, and with last dose on week 28.						

SC = subcutaneous

Sites and Regions:

This study is planned to be conducted globally at sites including but not limited to North America and Europe.

Data Monitoring Committee: For details on the Data Monitoring Committee, refer to Section 10.1.3, Appendix 1.

Statistical Analysis:

The primary analysis of the primary PK endpoints, area under the curve from time 0 over the dosing interval (AUC_{tau}) and maximum concentration (C_{max}), between weeks 28 and 30 will be performed based on the PK Parameter Analysis Set (consisting of all subjects who are randomized and received all assigned doses post-randomization and who have an evaluable ABP 501 or adalimumab serum concentration-time profile between weeks 28 and 30), according to the actual treatment groups (switching group versus continued-use group). The point estimates and 90% confidence intervals (Cls) for the GMRs between ABP 501 and adalimumab for AUC_{tau} and C_{max} between weeks 28 and 30 will be estimated using an analysis of covariance (ANCOVA) model adjusting for stratification factors, weight, and PK trough concentration at the end of the lead-in period (week 12). Prior to statistical modeling, the PK parameters will be logarithmically transformed (natural log). Point estimates and 90% Cls for the mean difference in logarithmic PK parameters will be estimated from the ANCOVA model, which will then be transformed back to the original scale to obtain the point estimates and 90% Cls for GMR. AUC_{tau} and C_{max} of ABP 501 and adalimumab between weeks 28 and 30 will be listed by subject

Final 1.0 Date: 03 Jun 2021 Page **14** of **87**

and summarized descriptively by treatment group. A sensitivity analysis of the primary PK endpoints will be conducted on the Per Protocol PK Parameter Analysis Set (consisting of all subjects from the PK Parameter Analysis Set who do not have an important protocol deviation that could affect the primary PK endpoints). To establish the risk in terms of safety or diminished efficacy of switching is not greater than the risk of using the reference product without such switch, the 90% CI of GMRs of ABP 501 versus adalimumab for AUC $_{tau}$ and C_{max} from the primary analysis should fall within the pre-specified similarity margin.

The analyses of the secondary PK endpoints of time of maximum concentration (t_{max}) between weeks 28 and 30 and trough concentration (C_{trough}) between weeks 14 and 28 will be based on the PK Parameter Analysis Set according to the actual treatment groups (switching group versus continued-use group). t_{max} will be summarized descriptively by treatment group and C_{trough} between weeks 14 and 28 will be summarized descriptively by visit and treatment group. The point estimates and 90% CIs for GMR for C_{trough} between the two treatment groups will be estimated using an ANCOVA model adjusting for stratification factors, weight, and PK trough concentration at the end of the lead-in period (week 12).

The analysis of the secondary efficacy endpoints will be based on the Per Protocol Efficacy Analysis Set (consisting of all subjects who are randomized and received all assigned doses post-randomization and who have not experienced an important protocol deviation that may affect the evaluation of the efficacy endpoints) according to the actual treatment groups (switching group versus continued-use group). The point estimate and 90% CI of the mean difference in Psoriasis Area and Severity Index (PASI) percent improvement from day 1 at week 30 will be estimated from an ANCOVA model adjusting for the baseline PASI value and the stratification factors. The point estimate and 90% CI of the risk differences in PASI 75, PASI 90 and PASI 100 response rates at week 30 will be estimated from a generalized linear model with an identity link adjusting for the stratification factors. Missing data will be imputed by last observation carry forward method for PASI percent improvement from day 1 at week 30 and by non-responder imputation for PASI 75, PASI 90 and PASI 100 response rates at week 30. In addition, the PASI percent improvement from day 1 at week 30 and PASI 100 response rates at week 30 will be summarized descriptively by treatment group.

All reported adverse events will be categorized by system organ class and preferred term according to the Medical Dictionary for Regulatory Activities (latest version at the time of final analysis) dictionary and graded by Common Terminology Criteria for Adverse Events, version

Clinical Study Protocol: 20200497

Final 1.0 Date: 03 Jun 2021 Page **15** of **87**

[figure not shown]
4.03. Safety analyses of the safety endpoints will be performed based on the Safety Analysis Set (consisting of all subjects who are randomized and receive any investigational product post randomization) according to the actual treatment received. Treatment-emergent adverse events post randomization are defined as adverse events that start or worsen on or after the first dose of investigational product post randomization and prior to the EOS. The numbers and percentages of subjects reporting treatment-emergent adverse events, serious adverse events and events of interests will be tabulated by treatment group. The number and percent of subjects developing binding or neutralizing antidrug antibodies (ADA) in the subset of Safety Analysis Set who have never tested positive (ie, tested negative or no results) prior to the first dose of investigational product post randomization and have at least one ADA result post randomization will be tabulated descriptively by treatment group and by visit.

In addition, safety analyses prior to randomization will be performed based on the Lead-in Treated Set (consisting of all enrolled subjects treated with at least 1 dose of investigational product during the lead-in period). The number and percentage of subjects reporting treatment-emergent adverse events, serious adverse events and events of interest while receiving adalimumab during the lead-in period will be summarized. The number and percentage of subjects developing binding or neutralizing ADAs for adalimumab during the lead-in period will be summarized.

Clinical Study Protocol: 20200497 Final 1.0 Date: 03 Jun 2021

1.2 Schema

^{*} Subjects with less than PASI 50 response at W12 will be discontinued

D: day = N: number of subjects; PK = pharmacokinetics; Q2W = every other week; SC = subcutaneous; W: week

Clinical Study Protocol: 20200497 Final 1.0 Date: 03 Jun 2021

Page 17 of 87

1.3 Schedule of Assessments

Table 1-1. Schedule of Assessments

									We	ek													
	Screen	Baseline	(+ 3 days) (± 3 days)											PK Endpoint Assessments Post Actual Week 28 Dose Date							End of Study (± 3 days) ^a		
Study Visit	≤ 28 days	Week 1/D ay 1	W2/ Day 8	4	6	8	10	12 ^j	14	16	18	20	22	24	26	28 ^b	+1d	+3d	+4d	+7d	+11d	+14d	32
Informed consent	Χ																						
Medical/medication history	Χ																						
Physical examination	Х	Χ																					Х
Height	Χ																						
Weight	Χ	Χ																					Х
Vital signs	Χ	Χ	Χ		Х			Χ		Х		Х				Х						Χ	Х
Adverse events	Xc	Χ	Χ	Х	Х	Χ	Х	Χ	Χ	Х	Χ	Х	Х	Х	Х	Х	Χ	Χ	Х	Χ	Χ	Χ	Х
Concomitant meds	Х	Χ	Х	Х	Х	Х	Х	Χ	Х	Х	Χ	Х	Х	Х	Х	Х	Χ	Х	Х	Χ	Х	Χ	Х
Disease assessments																							
PASI/sPGA/affected BSA	Χ	Χ			Χ			\mathbf{X}^{j}		Х		Χ										Χ	
Laboratory assessments																							
TB Testing ^d	Χ																						
Chest radiography ^e	Χ																						
TB worksheet ^f	Χ																						
Serology (HBsAg, HBcAb, HCV, HIV)	Х																						
Serum pregnancy test	Х																						
Urine pregnancy test		Χ			Х			Χ				Х				Х							Х
Hematology	Χ	Χ			Х			Χ				Х											Х
Chemistry	Х	Χ			Х			Χ				Х											Х
Urinalysis	Х	Χ																					Х
Pharmacokinetic sample ^h		Х			Х			Χ		Х		Χ				Χg	Χ	Χ	Χ	Χ	Χ	Χ	Х
Antidrug antibody sample ^h		Χ			Х			Χ		Х		Χ				Х						Χ	Х
Investigational product																							
Randomization								Χ															
IP administration ⁱ		Χ	Χ	Χ	Х	Х	Х	Χ	Χ	Х	Χ	Х	Х	Χ	Х	Χ							

Clinical Study Protocol: 20200497

Final 1.0 Date: 03 Jun 2021 Page **18** of **87**

BSA = body surface area; CT = computed tomography; HBcAb = hepatitis B core antibody; HBsAg = hepatitis B surface antigen; HCV = hepatitis C virus; HIV = human immunodeficiency virus; IP = investigational product; MRI = magnetic resonance imaging; PASI = Psoriasis Area and Severity Index; PK = pharmacokinetics; PPD = purified protein derivative; sPGA = static Physician's Global Assessment; TB = tuberculosis.

- ^a Subjects terminating early from the study should complete all procedures scheduled for EOS Visit (ie, week 32) within 28 days after withdrawal/discontinuation if possible.
- b Week 28 visit will have a window of ± 3 days.
- ^c Report serious adverse events that occur after signing informed consent form. Nonserious adverse events are reported as medical history prior to enrollment.
- d A QuantiFERON TB/T-spot or local equivalent will be performed. For the purposes of this study. Additional TB tests could be performed during the course of the study at the discretion of the investigator and according to local practice.
- ^e Chest radiograph will include anterior/posterior or posterior/anterior and lateral views. Historical films obtained or formal reports signed off by radiologist in the 3 months prior to screening are acceptable. Chest X-ray may be substituted by a chest CT or chest MRI, if available within 3 months prior to screening.
- Only for subjects with a positive tuberculosis test (ie, positive or indeterminate QuantiFERON, positive PPD).
- Pharmacokinetic sample will be collected as close to the nominal time points as possible. Study centers should strictly adhere to the tolerance windows outlined in the table below for week 28 through week 30 PK endpoint sample collection.
- h Pharmacokinetic and antidrug antibody samples should be drawn prior to investigational product administration at dosing visits (except 1 hour post week 28 dose pharmacokinetic sample).
- ABP 501 or adalimumab will be administered after all other procedures are completed for each visit. If the subject presents with an infection/adverse event at the dosing visit(s), the administration of investigational product may be delayed up to 5 days. In the case of delayed or missed dose, subsequent doses should be administered according to the original schedule (ie, at the planned time point relative to first dose/day 1). A minimum of 7 days must elapse between administrations of 2 doses.
- Subjects achieving less than PASI 50 response at week 12 visit will be considered non-responders and will be discontinued from the study at week 12. Subjects unable to complete the week 12 visit will be discontinued from the study. These subjects will be asked to complete an End of Study Visit procedures.

Table 1-2. Tolerance Windows for Pharmacokinetic Endpoint Sample Collection

Study Visit	Tolerance Windows ^a	
Week 28 predose	Within 3 hours prior to week 28 investigational product administration	
1 hour post week 28 dose	± 15 minutes	
1 day post week 28 dose	± 5 hours	
3 days post week 28 dose	± 6 hours	
4 days post week 28 dose	± 6 hours	
7 days post week 28 dose	± 6 hours	
11 days post week 28 dose	± 24 hours	
14 days post week 28 dose	± 48 hours	

PK = pharmacokinetic(s).

a. The week 28 visit and dose should be performed with a window of ± 3 days. Subsequent visits are done in relation to the actual week 28 investigational product dose date (eg, for the 3 days post week 28 dose time point, the PK sample should be collected 3 days after the actual week 28 dose, with a collection window of ± 6 hours).

Clinical Study Protocol: 20200497

Final 1.0 Date: 03 Jun 2021 Page **19** of **87**

2 Introduction

ABP 501 is Amgen's biosimilar product to Humira[®] (adalimumab). ABP 501 is approved in the United States (US) under brand name of AMJEVITA[™] (adalimumab-atto) and approved/marketed in European Union and other countries, as AMGEVITA[®] (adalimumab). [AMGEVITA[®] Summary of Product Characteristics (SmPC), March 2020, AMJEVITA[™] (adalimumab-atto) United States Prescribing Information (USPI), June 2019]. ABP 501 is approved as a 50 mg/mL formulation.

Amgen is now developing a new ABP 501 high concentration (mg/mL) formulation (referred to in this protocol as ABP 501-HCF). The dosage forms, route of administration (subcutaneous [SC]) and dosing regimens for ABP 501-HCF will be the same as those for the approved 50 mg /mL formulation;

ABP 501-HCF has not been approved or marketed anywhere. For specifics related to the minor differences in excipients between ABP 501 formulations and analytical comparability assessment please refer to the ABP 501 Investigator's Brochure.

Note that in this protocol the term "investigational product" refers to both, ABP 501-HCF or adalimumab (mg/mL approved formulation).

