6.7 Dose Modification

There are no dose modifications for investigational products (ABP 501 or adalimumab) in this study.

If the subject presents with a serious infection at the dosing visit(s), the administration of investigational product may be delayed (up to 5 days); and subjects with serious infections need to be monitored closely and investigational product should not be administered until the infection resolves.

In the case of delayed or missed dose for any reason, subsequent doses should be administered according to the original schedule (ie, at the planned time point relative to first dose) investigational product dose(s).

Any toxicities associated or possibly associated with investigational product treatment should be managed according to standard medical practice. A summary of expected adverse drug reactions is provided in the Investigator's Brochure. Adalimumab has a terminal -half-life of approximately 14 days, therefore discontinuation results in slow elimination over several months and will have no immediate effect.

If unmanageable toxicity due to investigational product occurs at any time during the study, treatment with the investigational product should be discontinued.

Clinical Study Protocol: 20200497

Final 1.0 Date: 03 Jun 2021 Page **39** of **87**

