8.3.4 Documenting and Reporting of Adverse Events

The investigator is responsible for ensuring that all adverse events observed by the investigator or reported by the subject that occur from the time of enrollment through the EOS Visit are recorded in subject's medical records as well as the applicable CRF Adverse Event Summary page. The adverse event grading scale to be used for this study will be CTCAE version 4.03, as described in Section 8.3.2.1.

The investigator must assign the following adverse event attributes:

- Adverse event diagnosis or syndrome(s), if known (if not known, signs or symptoms)
- Dates of onset and resolution
- Severity (National Cancer Institute CTCAE version 4.03)
- Assessment of relatedness to investigational product, other protocol required therapies or devices
- Action taken

The investigator must assess whether the adverse event is possibly related to the investigational product. This relationship is indicated by a "yes" or "no" response to the question: "Is there a reasonable possibility that the event may have been caused by the investigational product?" The investigator is responsible for reviewing laboratory test results and determining whether an abnormal value in an individual study subject represents a clinically significant change from the subject's baseline values. In general, abnormal laboratory findings without clinical significance (based on the investigator's judgment) are not to be recorded as adverse events. However, laboratory value changes that require treatment or adjustment in

Clinical Study Protocol: 20200497 Final 1.0 Date: 03 Jun 2021

current therapy are considered adverse events. Where applicable, clinical sequelae (not the laboratory abnormality) are to be recorded as the adverse event.

The investigator's clinical judgment is used to determine whether a subject is to be removed from treatment due to an adverse event. A subject, or subject's legal representative, can also voluntarily withdraw from treatment due to an adverse event. If the subject withdraws consent, the subject is encouraged to undergo, at a minimum, an EOS assessment.

It is the investigator's responsibility to review all documentation (eq. hospital notes, laboratory reports, and diagnostic reports) related to an adverse event. Wherever possible, the investigator's diagnosis, not the individual signs and symptoms, will be documented as the adverse event

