8.3.4.3 Reporting of Serious Adverse Event After the Protocol Required Reporting Period

There is no requirement to monitor study subjects for serious adverse events following the protocol required reporting period or after the EOS. However, these serious adverse events can be reported to Amgen. Per local requirements in some countries, investigators are required to report serious adverse events that they become aware of after the EOS. If serious adverse events are reported, the investigator is to report them to Amgen within 24 hours following the investigator's knowledge of the event.

Serious adverse events reported outside of the protocol-required reporting period will be captured within the safety database as clinical study cases and handled accordingly based on relationship to investigational product.

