3.1 Study Design

This is a randomized, double-blinded, phase 3 study in adult subjects with moderate to severe plaque psoriasis. This study is planned to be conducted globally at study centers including but not limited to North America and Europe.

The total duration of study participation for each subject will be about 36 weeks, with up to 4 weeks for screening and approximately 32 weeks after the first investigational product administration.

Subjects will receive an initial 6 doses of Humira on week 1 (day 1) mg loading dose), 1 week later on week 2 mg), then 2 weeks later on week 4, week 6, week 8, and week 10 mg), administered subcutaneously (SC). At week 12, subjects will be randomized to either the continued use group or switching group in a 1:1 ratio, stratified by geographic region and prior biologic use at baseline (week 1/day 1, yes vs. no). Subjects in the continued use group will stay on Humira Q2W with last dose at week 28 and subjects in the switching group will switch to ABP 501 Q2W at week 12 (dosed week 12 and week 14), then back to Humira Q2W at week 16 (dosed week 16 and week 18), and again to ABP 501 Q2W at week 20, (dosed week 20, week 22, week 24, week 26, and last dose at week 28).

At Week 12, efficacy assessments will be conducted including evaluation of PASI.

Protocol Number: 20200497

Date: 10FEB2023 Page 11 of 36

Subjects who do not achieve a PASI 50 response or better improvement at Week 12 are considered as non-responders and will not be randomized at Week 12; these subjects will complete End of Study (EOS) procedures at Week 12. The Lead-in Period will occur from day 1 until prior to randomization at Week 12. Those unable to complete the Week 12 visit will be discontinued from the study. All enrolled subjects not randomized at Week 12 will be considered lead-in failures and the lead-in failure reason will be documented.

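### Adverse event collection ends at the EOS visit, which has no minimum time from last dose for subjects who leave the study early: about 0 to 42 days is permitted, against 28 for completers

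*Protocol*

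**What the plan says.** **End of collection.** Protocol 8.3.4 requires that AEs "that occur from the time of enrollment through the EOS Visit are recorded". Serious AEs (SAEs) are reported from consent to the same visit (8.3.4.1). After that, Protocol 8.3.4.3 states: "There is no requirement to monitor study subjects for serious adverse events following the protocol required reporting period or after the EOS". The treatment-emergent (TEAE) windows in Protocol 9.5.3 and 9.5.4.2 and in SAP 5.4 also close at EOS, and SAP 5.1 takes the EOS date from the CRF.

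**Completers.** The last dose is at week 28 and EOS is at week 32 (Protocol 6.8).

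**Subjects who leave the study early.** The only timing rule is Table 1-1 footnote a, repeated in Section 7.2: "Subjects terminating early from the study should complete all procedures scheduled for EOS Visit (ie, week 32) within 28 days after withdrawal/discontinuation if possible".

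**PASI 50 non-responders at week 12.** The protocol gives no day in the Table 1-1 footnote on this group: "These subjects will be asked to complete an End of Study Visit procedures". SAP 3.1 does give one: "these subjects will complete End of Study (EOS) procedures at Week 12". SAP Section 10 does not list this as a change from the protocol.

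**Subjects who stop product only.** Protocol 7.1 recommends that they stay in the study for safety surveillance, and it lists telephone contact among the follow-up options.

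**Exposure after stopping.** Protocol 6.7 gives a terminal half-life of about 14 days and adds: "therefore discontinuation results in slow elimination over several months and will have no immediate effect".

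**The concern.** The length of safety observation after the last dose is fixed by design for completers and left to visit scheduling for early leavers. An EOS visit on the day of withdrawal complies with footnote a. On the protocol's own half-life, such a subject leaves observation while still substantially exposed, and no one is required to look for new events after that.

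The safeguards elsewhere do not close this gap. Section 8.3.4.5 follows events already reported. Section 8.3.4 requires notification of a post-discharge SAE only if the investigator happens to learn of it and considers it related. New non-serious events, and SAEs that nobody volunteers, are missed.

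What is at stake is the completeness of the TEAE, SAE and event-of-interest incidences. SAP 9.7.1 compares events of interest by risk differences on subject counts, with Wald or exact limits and no stated adjustment for observation time, so unequal follow-up would go uncorrected. The protocol already ties one safety item to the last dose: pregnancies are collected until 5 months after the last injection (8.3.5). AE collection has no such tie.

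**Working it through.** **1. The plan's own counts.** Inputs from Protocol 9.3: 414 enrolled, 17% lead-in failures, 342 randomized, 15% drop-outs.
- Enrollment: 342 / (1 − 0.17) = 412.05, rounded up to 413, against 414 stated. The figure reproduces.
- Lead-in failures: 0.17 × 414 = 70.4, about 70 (414 − 342 = 72 by subtraction).
- Post-randomization drop-outs: 0.15 × 342 = 51.3, about 51. By the plan's definition this includes subjects who reach week 28 but lack evaluable PK, so it is an upper bound on early leavers.

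**2. Study days.** Day 8 is week 2 and visits from week 4 are 14 days apart, so week 10 is day 64 and week 12 is day 78. Week 28 is day 190 and week 32 is day 218. The SAP 5.1 target days for weeks 12, 28 and 32 agree.

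**3. Last dose to end of AE collection.**

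| Subject | Calculation | Days |
|---|---|---|
| Completer | 218 − 190 | 28 nominal (22 to 34 with ±3 days on both visits) |
| Week 12 non-responder, SAP 3.1 | 78 − 64 | 14 nominal (8 to 20 with ±3 days on both visits) |
| Week 12 non-responder, protocol footnote a | 14 + (0 to 28) | 14 to 42 |
| Other early leaver, footnote a | (0 to 14) + (0 to 28) | 0 to 42 |

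The last row assumes that withdrawal falls within one 14-day dosing interval of the last dose taken. Because the 28 days apply only if possible, a later EOS can also occur.

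**4. Exposure at those times.** Assume simple decay with the stated 14-day half-life, so the share of the last dose remaining is 0.5^(t/14): 100% at day 0, 50% at day 14, 25% at day 28 and 12.5% at day 42.

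Allowing for earlier doses, and assuming equal maintenance doses and a loading dose of two units, the levels in units of one maintenance dose are:
- Steady-state trough: 0.5 + 0.25 + 0.125 + … = 1.00.
- Week 12, before any dose: 0.5 + 0.25 + 0.125 + 0.0625 + 0.03125 + 2 × 0.5^(77/14) = 1.01.
- Week 32: 0.25 + 0.125 + … = 0.50.

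A week 12 EOS therefore closes collection at about the full trough level, against about half of it for a completer. This contrast is specific to a week 12 EOS and does not describe all early leavers.

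**5. Which summary is touched.** Lead-in failures are never randomized. Their missed events reduce only the lead-in summary, which Protocol 9.1 presents as one group. Only post-randomization leavers enter the comparison between arms.

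**The case against.** The strongest reply is that the plan gives early leavers adequate follow-up and the gap is narrow.

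- Footnote a allows EOS up to 28 days after withdrawal, so some leavers are watched as long as completers or longer. This stands: the permitted range is 0 to 42 days. A reader might infer that early leavers get only 0 to 14 days, but that holds only if EOS is held on the day of withdrawal.
- The zero end is extreme. Product is given after all other procedures at a visit (Protocol Section 8), so someone who withdraws at a scheduled visit before dosing is already about 14 days past the last dose. This stands as to what is typical. It does not supply a minimum.
- A reader might infer that subjects who stop product because of an adverse event get the shortest window. Section 7.1 says otherwise: they should not be removed automatically and are encouraged to remain. The gap concerns those who leave the study. Some of these withdraw consent or are lost to follow-up, and a phone call will not recover them. Non-responders, however, have to leave.
- SAP 3.1 is a design summary, and the EOS date comes from the CRF. If sites hold EOS later, the window lengthens accordingly. This stands: the SAP sentence does not itself shorten collection. It is a mismatch to reconcile.
- Twenty-eight days is also short against elimination over months. This is true, but the case for 28 days is parity with completers, not completeness.
- Reported events are followed up, and related SAEs that become known later are notified. Both are useful, but neither finds new events systematically.

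**Conclusion.** The point holds as a cheap improvement. AE and SAE collection and the TEAE windows end at an EOS visit that, for early leavers, has no minimum time from the last dose. About 0 to 42 days is permitted (14 nominal for non-responders under SAP 3.1, 14 to 42 under the protocol), against 28 nominal for completers. The range rests on withdrawal within 14 days of a dose and on EOS within the 28-day limit.

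The number affected is not known. It is an unstated share of about 70 lead-in failures and of at most about 51 post-randomization drop-outs. A reader might add these and say that nearly 30% of enrolled subjects are under-observed. The documents do not support that: both figures are upper bounds, the 51 includes subjects lost only for PK reasons, and nothing says how many leavers have an early EOS.

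A reader might also infer a biased comparison between arms. That would need study withdrawal to differ by arm, which the documents do not suggest. For lead-in failures it cannot arise. The sample size and the primary PK analysis are untouched.

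**What to change.** 1. In Table 1-1 footnote a, Section 7.2 and Section 8.3.4, state that for early leavers and lead-in failures who have not withdrawn consent, AEs and SAEs are collected until at least 28 days after the last dose, matching completers. This is done at the EOS visit, or by one phone contact if EOS came earlier.
2. In Protocol 9.5.3 and 9.5.4.2 and SAP 5.4, let the TEAE window for these subjects end at the later of EOS and last dose + 28 days.
3. Reconcile SAP 3.1 with the protocol on when the non-responders' EOS takes place.

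Cost: a short amendment and at most one call per affected subject, with no added procedures. The downside is that some events in the added days may follow the start of alternative therapy (Protocol 6.6.2 places this after EOS). These must be flagged so that they can be shown separately.
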